### 9.3.3. Endpoints of Interest

For the interim and final safety reports (which will include information on patients, covariates and incidence rates for pre-specified safety outcomes, from SRQ as well as from the linked Patient/Prescribed Drug and other registers), the following events of interest have been pre-specified.

1. Hospitalised infections overall.
2. NMSC.
3. Malignancies, excluding NMSC.
4. CV events, including but not limited to deep vein thrombosis/pulmonary embolism.
5. Use during pregnancy.

In addition, the final study report will include the number of Ruxience-exposed pregnancies. If data are sufficient, rates of diagnosed malformations can be provided however, the number of Ruxience-exposed pregnancies is expected to be low based on previous data for other biosimilars.

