**Table 1. Temporal Trends in the Percentage Use of Biosimilars in ARTIS**

Year	Adalimumab	Etanercept	Infliximab	Rituximab
2010	0	0	0	0
2011	0	0	0	0
2012	0	0	0	0
2013	0	0	0	0
2014	0	0.1%	0	0
2015	0	0.4%	57%	0
2016	0	81%	75%	0
2017	0	74%	92%	0
2018	7%	17%	88%	42%

The treating physicians enter the information into the study data-base via a web-based interface. Optionally, it is possible to send the data to the study secretariat on a pre-designed paper form. Patients can enter his/her data through the internet ahead of the visit, at touch-screens in the waiting room, or on paper. The clinical information can be accessed by the treating physician and has been found to be a very useful tool in the management of individual patients. Currently, the vast majority of the rheumatologist-derived data are entered directly via the internet in direct conjunction with the visit, and over half of the patient-derived data are also entered electronically, ahead of the visit.

Safety outcomes included in ARTIS are derived from 2 sources; spontaneous reports of adverse drug reactions (ADRs), and linkage to the national health care registers of Sweden (Section 9.4.2). This study will only utilise the data describing health outcomes derived from national health care registries.

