**Table 2. Precision Estimates Based on Incidence Proportions for Safety Events Reported in the Ruxience RMP**

Condition	Incident Count	Population at Risk	Incidence Proportion	Lower Bound of 95% CI	Upper Bound of 95% CI
Any infection (including serious infection)	22	73	0.301	0.199	0.420
Serious infection	3	73	0.041	0.009	0.115
Malignancy (excluding NMSC)	1	73	0.014	0.000	0.074
NMSC	0	73	0.000	0.000	0.049
CV events	3	73	0.041	0.009	0.115

NMSC, non-melanoma skin cancer; CV, cardiovascular; CI, confidence interval.

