## 9.7. Data Analysis

All statistical analyses will be performed by ARTIS using SAS version 9.4 or later. Detailed methodology for all analyses of data included in this study will be documented in a Statistical Analysis Plan (SAP), which will be dated, filed and maintained by ARTIS and shared with the Sponsor. The SAP may modify the plans outlined in the protocol; any major modifications of primary endpoint definitions or their analyses would be reflected in a protocol amendment.

ARTIS will apply an ICD-code-based algorithm to identify serious infections, malignancies and CV events (MACE), in the Swedish patient register. See [Table 3. Endpoint Algorithms and Validation References](#) in [ANNEX 1. LIST OF STAND ALONE DOCUMENTS](#) for algorithms and relevant validation references. The specific algorithms for defining those endpoints have not been validated, though the Swedish patient register has been validated several times. The overall positive predictive value (PPV) of the inpatient diagnoses generally ranged from 85% to 95%. A regional validation study of hospitalised acute MI and stroke (components of the MACE endpoint) found PPVs of 96% and 94% respectively, in the period 1977 to 1987. While the ICD algorithms used by ARTIS to define the endpoints of interest may not be validated, their use can be justified given the importance to contextualise the study results with historical findings. ARTIS has previously conducted and published studies of serious infections  and MACE  events in RA patients.

Per Pfizer's subscription to the ARTIS database, analyses will be conducted by ARTIS researchers and in accordance with ARTIS scientific review policies. The database does not contain any patient identification information (eg, name), except for a unique number assigned for the purpose of linking files.

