CV Risk	Major Acute Cardiovascular Events (MACE), combines MI, stroke, and fatal cardiovascular events: I00-I99 as main cause of death, or I20.0, I21, I60-I64 as diagnosis in in- or outpatient care	
‘Outcome’ was defined as any first-ever ACS event, which in turn was defined as a primary discharge diagnosis of acute myocardial infarction or unstable angina pectoris, or as acute myocardial infarction being the underlying cause of death. For discharge diagnoses, the date of admission to hospital was considered the event date. This outcome definition has previously been validated in a Swedish early RA cohort, with a positive predictive value of 95%. In addition, a regional validation study of hospitalised acute MI and stroke found positive predictive values of 96% and 94% respectively, in the period 1977 to 1987.
 
References:  https://onlinelibrary.wiley.com/doi/epdf/10.1002/art.39267            Mantel et al. Risk Factors for the Rapid Increase in Risk of Acute Coronary Events in Patients With New-Onset Rheumatoid Arthritis. A Nested Case-Control Study. Arthritis & Rheumatology. 2015; 67(11):2845-2854.
 
Lindblad et al. Validity of register data on acute myocardial infarction and acute stroke. Scandinavian Journal of Public health 1993; 21 (1):3-9.

NMSC	
Identified through the Cancer register as all malignancies with ICD-O/2 code C44, and all basal cell cancers recoded in the register’s subcomponent on basal cell cancers
 
Alt: all invasive NMSC, identified as non-benign ICD-O/2 code C44, and no basal cell cancers.
	
About 99% of cancers have been morphologically verified. Reporting of incident cancers (including invasive malignancies as well as cancer in situ) is mandatory and semi-automated, resulting in an estimated coverage greater than 95%.

090177e1953e1418\Approved\Approved On: 16-Oct-2020 13:21 (GMT)

Event	Operationalisation	Validation ICD
Malignancy	All invasive malignancies recorded in the cancer register, excluding NMSC	See NMSC
Abbreviations: ACS= acute coronary syndrome; ARTIS= Anti Rheumatic Treatment in Sweden; ICD= International Classification of Diseases; MACE= major acute cardiovascular events; MI= myocardial infarction; NMSC= non-melanoma skin cancer; RA= rheumatoid arthritis		

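### Section 9.3.3 counts DVT/PE as a cardiovascular endpoint, but the only CV algorithm (Table 3) captures it solely as a main cause of death, so as written every non-fatal DVT/PE is missed

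*Protocol*

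**What the plan says.** Three places in the protocol define the cardiovascular endpoint.

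- **Section 9.3.3, item 4**, in the list of pre-specified events for the interim and final reports: "CV events, including but not limited to deep vein thrombosis/pulmonary embolism". DVT/PE is the only cardiovascular component named, and the wording leaves the rest open.
- **Section 9.7**: "ARTIS will apply an ICD-code-based algorithm to identify serious infections, malignancies and CV events (MACE), in the Swedish patient register". The same paragraph points to Table 3 "for algorithms and relevant validation references".
- **Annex 1, Table 3**, the row on CV risk: "Major Acute Cardiovascular Events (MACE), combines MI, stroke, and fatal cardiovascular events", operationalised as "I00-I99 as main cause of death, or I20.0, I21, I60-I64 as diagnosis in in- or outpatient care".

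Section 9.2.3, in the text after Table 1, restricts the source of outcomes: "This study will only utilise the data describing health outcomes derived from national health care registries". Spontaneous adverse reaction reports are therefore not used.

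**The concern.** The endpoint list and the algorithm assigned to it describe different things. Item 4 tells the reader that DVT/PE is looked for. Section 9.7 and Table 3 define a composite of myocardial infarction, stroke and cardiovascular death, and venous thromboembolism is not among its non-fatal components. An analyst cannot follow both.

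The study has no comparator and tests no hypothesis. Its product is a set of single-cohort incidence rates, so the event definition settles what each number means. Impact on cardiovascular disease is one of the risk management plan topics that sections 4 and 7 give as the reason for the study. If a MACE rate were reported under the heading of CV events, a reader of section 9.3.3 would take it to include DVT/PE. The definition also affects the denominator: section 9.3.2 follows each patient until the outcome in question, so person-time depends on what counts as an event.

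**Working it through.** **The protocol's only CV figure.** Table 2 ("Precision Estimates Based on Incidence Proportions for Safety Events Reported in the Ruxience RMP") gives 3 CV events among 73 patients, proportion 0.041, 95% CI 0.009 to 0.115.

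- Proportion: 3/73 = 0.0411.
- Exact (Clopper-Pearson) limits: lower = 2.5% quantile of Beta(3, 71) = 0.0086; upper = 97.5% quantile of Beta(4, 70) = 0.1154.

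This agrees with Table 2. The row does not split CV events by type, so it says nothing about how many were DVT/PE. It is context only, and the point does not depend on it.

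**The definitions side by side.** The relevant ICD-10 categories are I26 (pulmonary embolism) and I80-I82 (venous thrombosis). These meanings come from the classification; the protocol does not spell them out.

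| Category | In the in-/outpatient list (I20.0, I21, I60-I64)? | In the cause-of-death range (I00-I99)? |
|---|---|---|
| I26 | No | Yes |
| I80 | No | Yes |
| I81 | No | Yes |
| I82 | No | Yes |

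Two consequences follow.

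1. A non-fatal DVT or PE meets neither branch and contributes no event.
2. A fatal one counts only if it is recorded as the main cause of death.

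The same result follows without the codes. Table 3 describes the composite in words as MI, stroke and fatal cardiovascular events, which leaves no place for a non-fatal venous event.

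**Other routes.** The remaining rows of Table 3 cover serious infections, NMSC and other malignancies, and none includes DVT/PE. No other section gives a DVT/PE algorithm. Section 9.2.3 rules out spontaneous reports as a source. As the protocol stands, nothing supplies these events.

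**The case against.** The strongest reply is that section 9.7 leaves detailed methods to an SAP, which may modify the protocol's plans and is not shown. A DVT/PE code list there, applied to the registers already linked, would satisfy item 4. This stands as a limit on prediction: a reader might infer that the final report will contain no non-fatal DVT/PE, and the protocol alone does not establish that. It does not remove the contradiction. The protocol has already fixed a code list, and that list conflicts with its own endpoint. An SAP that follows either place departs from the other.

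Three further readings go beyond the documents.

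- **That Table 3 has no DVT/PE code at all.** It does: the I00-I99 cause-of-death range spans these codes. The gap is in the in-/outpatient list.
- **That the CV rate is understated by a stated percentage.** If VTE occurred at a ratio r to MACE, the missed share would be r/(1 + r): 9% at r = 0.1 (0.1/1.1), 33% at r = 0.5 (0.5/1.5) and 50% at r = 1 (1/2). The protocol gives neither rate, so no value of r can be preferred. The formula also adds the two event types, whereas a patient with both would count once in a first-event composite.
- **That the report would give false reassurance.** Section 9.7 and Table 3 both use the MACE label, and a report that kept it would not mislead. The harm arises if the rate is headed CV events without a definition. Nothing shown ties VTE specifically to the risk management plan's cardiovascular risk, and section 7 describes the study as voluntary.

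It is also fair to say that restating item 4 as MACE alone would remove the contradiction. It would do so by dropping the one cardiovascular event that the list names.

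**Conclusion.** The point holds as a contradiction within the protocol. Item 4 of section 9.3.3 includes DVT/PE, while the only algorithm assigned to it captures DVT/PE solely as a main cause of death. Followed as written, Table 3 misses all non-fatal DVT/PE and yields a MACE rate, which is not the pre-specified endpoint.

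The finding is structural. No numerical size can be attached to the undercount, because the protocol contains no VTE rate. The conclusion rests on reading Table 3 as the operative definition, which is how section 9.7 presents it, and on the standard ICD-10 meaning of I26 and I80-I82. It makes no claim about what the SAP contains.

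A code row alone would not fully settle the matter. The open-ended wording of item 4 would still leave the endpoint broader than any finite code list, so that wording needs to change too.

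**What to change.** 1. Add a VTE row to Table 3 with the ICD-10 codes for DVT and PE (for example I26 and I80-I82, with ARTIS settling the subcodes). State the care setting (inpatient, outpatient or both) and the diagnosis position (main or any).
2. Report VTE and MACE as two separately labelled rates in the interim and final reports. Do not fold VTE into MACE: section 9.7 justifies these algorithms by the need to set the results beside earlier ARTIS work, and a changed composite would lose that.
3. Reword section 9.3.3, item 4, and the matching sentence in section 9.7 as a closed list: MACE; DVT/PE.

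The cost is one more code list and one more results row. The Patient Register, with inpatient and non-primary outpatient diagnoses, is already linked (sections 9.3 and 9.4.3), so no new data source is needed.

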## 9.4. Data Sources

### 9.4.1. SRQ

SRQ is the source of disease activity information, measured by C-reactive protein (CRP), erythrocyte sedimentation rate (ESR), health assessment questionnaire (HAQ), number of swollen and tender joints, and patient's global assessment of disease (on a visual analog scale (VAS)) and doctor's evaluation on a Likert type scale. In addition, Disease Activity Score in 28 joints (DAS28), the European league against rheumatism response criteria, and the American College of Rheumatology criterion of improvement (ACR 20 50) can be calculated.

### 9.4.2. SRQ/ARTIS Linkage

Endpoint information will be derived from the linkage of SRQ/ARTIS to nationwide Swedish health care registers. The register linkage has many advantages in providing data on all comorbidities that have been diagnosed. The drawback is a lag time of between 1 and 2 years from when an event occurs until it can be analysed and reported using the national health care registers. This delay is caused by the annual curation of the Patient and Cancer registers by the National Board of Health and Welfare (ie, data from each year is only made available after internal processing, usually 9 to 12 months later, and the processing of data requests.

#### **9.4.3. The Patient Register and the Prescribed Drug Register**

The Swedish Patient Register provides information on all hospitalised (inpatient treated) patients, and all visits to non-primary outpatient care (such as a visit to a rheumatologist). Diagnoses are assigned by the discharging/treating physician, as well as date of discharge/visit, hospital and department. Diagnoses are coded according to the International Classification of Diseases (ICD), with version 8 used until 1986, version 9 1987 to 1996 and ICD10 since 1997.

The Prescribed Drug Register provides all retrievals of prescribed drugs in Sweden from July 2005 and may be used to aid correct classification of patients by their history of retrieved DMARDs.

#### **9.4.4. The Swedish Cancer Register**

The Swedish Cancer Register was established in 1958 and provides data on date of cancer (and some selected pre-cancers) onset, and type of cancer according to the ICD classification and morphology/histology. About 99% of cancers have been morphologically verified. Reporting of incident cancers (including invasive malignancies as well as cancer in situ) is mandatory and semi-automated, resulting in an estimated coverage greater than 95%.

#### **9.4.5. The Medical Birth Register**

The Medical Birth Register contains prospectively collected data from antenatal, obstetric, and neonatal records since 1973, and covers all live and still births (but not all miscarriages) in Sweden. Among the variables covered are maternal age, parity, smoking and family situation in early pregnancy, and the infant's birth weight and length, gestational age (primarily based on ultrasound dating), and Apgar score. Complications and mother's and infant's morbidities are coded according to the ICD, with version 8 used until 1986, version 9 1987 to 1996 and ICD10 since 1997.

#### **9.4.6. The Cause of Death Register**

The Cause of Death Register is a national register containing information on date and cause of death (underlying and contributory) for all deceased residents, including deaths among Swedish residents who died abroad. Although the register was started in 1952, the data is considered complete since 1961.

#### **9.4.7. The Total Population Register**

The Total Population Register lists data on residency at a given point in time since it was founded in 1961, and dates of emigration/immigration for all subjects ever resident in Sweden since 1961. This register thus provides information on censoring (death and emigration) of study subjects and can also be used to identify a general population comparison cohort.

## 9.5. Study Size

All eligible patients in ARTIS who initiate Ruxience during the study period will be included, with no upper limit on the sample size. This is a descriptive study with no a priori hypotheses. Table 2 displays 95% confidence intervals around the incidence proportions for safety events of interests reported in the Ruxience RMP.

**Table 2. Precision Estimates Based on Incidence Proportions for Safety Events Reported in the Ruxience RMP**

Condition	Incident Count	Population at Risk	Incidence Proportion	Lower Bound of 95% CI	Upper Bound of 95% CI
Any infection (including serious infection)	22	73	0.301	0.199	0.420
Serious infection	3	73	0.041	0.009	0.115
Malignancy (excluding NMSC)	1	73	0.014	0.000	0.074
NMSC	0	73	0.000	0.000	0.049
CV events	3	73	0.041	0.009	0.115

NMSC, non-melanoma skin cancer; CV, cardiovascular; CI, confidence interval.

## 9.6. Data Management

This study analyses existing data within the ongoing ARTIS register. The ARTIS researchers are responsible for the data management of this study. As previously described, health and demographic information within Sweden is collected in a series of registers with a high degree of completeness resulting from the mandatory and semi-automated registration of their data. Based on each Swedish resident's unique personal identification number, issued to all Swedish residents alive in 1947 or born/immigrated thereafter, linkage of data from different registers is possible. The registers are maintained by governmental bodies (the main registers used in this project are held by the National Board of Health and Welfare (Socialstyrelsen) and Statistics Sweden (Statistiska centralbyrån), who may perform data linkages and provide de-identified data for research purposes.

The data warehouses of ARTIS reside on restricted, double backed-up, servers at the Clinical Epidemiology unit at the Karolinska University Hospital Campus. ARTIS data are housed at the Clinical Epidemiology Division and linked to the data received from the National Board of Health and Welfare and/or Statistics Sweden using the unique personal identification number that all Swedish residents receive. Trained staff perform this linkage, in addition to data cleaning and analysis. All work with these data warehouses is done by trained staff in adherence with local guidelines on good programming and data management practices, and on archiving. Data, programs, and documents related to study reports will be maintained for a minimum of ten years.

## 9.7. Data Analysis

All statistical analyses will be performed by ARTIS using SAS version 9.4 or later. Detailed methodology for all analyses of data included in this study will be documented in a Statistical Analysis Plan (SAP), which will be dated, filed and maintained by ARTIS and shared with the Sponsor. The SAP may modify the plans outlined in the protocol; any major modifications of primary endpoint definitions or their analyses would be reflected in a protocol amendment.

ARTIS will apply an ICD-code-based algorithm to identify serious infections, malignancies and CV events (MACE), in the Swedish patient register. See [Table 3. Endpoint Algorithms and Validation References](#) in [ANNEX 1. LIST OF STAND ALONE DOCUMENTS](#) for algorithms and relevant validation references. The specific algorithms for defining those endpoints have not been validated, though the Swedish patient register has been validated several times. The overall positive predictive value (PPV) of the inpatient diagnoses generally ranged from 85% to 95%. A regional validation study of hospitalised acute MI and stroke (components of the MACE endpoint) found PPVs of 96% and 94% respectively, in the period 1977 to 1987. While the ICD algorithms used by ARTIS to define the endpoints of interest may not be validated, their use can be justified given the importance to contextualise the study results with historical findings. ARTIS has previously conducted and published studies of serious infections  and MACE  events in RA patients.

Per Pfizer's subscription to the ARTIS database, analyses will be conducted by ARTIS researchers and in accordance with ARTIS scientific review policies. The database does not contain any patient identification information (eg, name), except for a unique number assigned for the purpose of linking files.

### 9.7.1. Annual Reports

Reports summarising Ruxience uptake and patient characteristics will be provided on an annual basis. These will provide data from SRQ/ARTIS on patients treated with Ruxience.

### 9.7.2. Interim and Final Study Reports

The interim and final reports will present data on safety events of interest identified through linkages with the patient, cancer, and death registers as appropriate.

For these analyses, the Ruxience cohort will be analysed overall and stratified by previous biologics use. The general analytic approach will be descriptive and include incidence rates of events of interest within the Ruxience cohort. Incidence rates will be calculated by dividing the number of events by the person-time of exposure and will include 95% confidence intervals.

## 9.8. Quality Control

This study uses data existing within ARTIS. ARTIS works mainly with data from the SRQ, a quality of care register with several guidelines in place to monitor and maintain data quality. Physicians working with the SRQ have access to an online portal in which they can monitor all their patients and their information. Regional representatives encourage/remind the physicians to check the quality of the information by accessing the “Data Quality” section of the “Visit monitoring” tool: in this section a series of questions guide the doctor in checking the quality of the registered information of their patients. Moreover, the data coordinator of SRQ periodically check the quality of the data overall in the region.

## 9.9. Limitations of the Research Methods

This study is designed to monitor the safety of Ruxience in the clinical practice setting utilising the ARTIS Register, a well-established Swedish-based rheumatology register. Despite the strengths of the register, data must be evaluated in light of their limitations. For example, consistent with most observational studies, the possibility of endpoint misclassification, is of concern in interpreting findings.

As a new therapy in the RA treatment armamentarium, it is possible that patients treated with Ruxience will represent those with the most severe cases of disease, longer disease duration, history of multiple failed RA therapies and physical comorbidities that place patients at risk for events. Biases resulting from channeling may present as increased rates of safety events of interest in the early phases of the study. Stratification on key indicators of disease severity, patient characteristics and past therapies can be done for contextualisation. Trend analyses may be conducted to evaluate rates in Ruxience patients over time.

The RA treatment landscape has evolved over time with the introduction of new therapies, treatment recommendations, and approaches to patient management. The rates of safety events of interest and their distribution among patient-types may have changed over time.

Endpoint misclassification is of particular concern within the observational setting due to less stringent monitoring relative to clinical trials. While ARTIS has an established system to identify and capture endpoint data, all events cannot be fully verified via source documentation. Instead, linkage to national health care registers allows the register to obtain data on all safety events of interest (regardless of suspected causal relationship to the treatments).

Another limitation of this study design is the absence of a control group which does not allow for comparative analysis of incidence rates with other treatments. This study will follow patients for a period of 3-years from therapy initiation, assuming continued participation and sufficient accrual of Ruxience patients is feasible. This period of follow-up may not be sufficient to adequately evaluate all safety events of interest, specifically malignancies. Conclusions may not be generalisable outside of the 3-year period since initiation of therapy.

